6.4.4 Rescue Medications & Supportive Care

Participants should receive appropriate supportive care measures as deemed necessary by the treating investigator. Suggested supportive care measures for the management of AEs with potential immunologic etiology are outlined along with the dose modification guidelines in Section 5.2 [Table 5.2-1]. Where appropriate, these guidelines include the use of oral or IV treatment with corticosteroids, as well as additional anti-inflammatory agents if symptoms do not improve with administration of corticosteroids. Note that several courses of steroid tapering may be necessary as symptoms may worsen when the steroid dose is decreased. For each disorder, attempts should be made to rule out other causes such as metastatic disease or bacterial or viral infection, which might require additional supportive care. The treatment guidelines are intended to be applied when the investigator determines the events to be related to pembrolizumab.

It may be necessary to perform conditional procedures such as bronchoscopy, endoscopy, or skin photography as part of evaluation of the event.

Given that pembrolizumab may reactivate anti-BCMA CAR-Ts, there is a theoretical risk for development of cytokine release syndrome (CRS). CRS is a well-known side-effect of CAR-T therapies and is characterized by systemic inflammation, fever, and organ dysfunction due to immune activation. Clinical manifestation of CRS includes high fevers, hypotension, tachypnea, hypoxia, confusion, fatigue, nausea, vomiting, headache, evidence of disseminated intravascular coagulation, and macrophage activation syndrome. The etiology of CRS is thought to be secondary to increased inflammatory cytokines and activation of T-lymphocytes,

macrophages, and endothelial cells. These factors are important for activation and clonal expansion of CAR-T therapies and thus some degree of CRS is to be expected with CAR-T therapy. However, in some cases, the over-activation of immune responses may be associated with significant organ dysfunction, and thus therapies, including anti-inflammatory and anti-cytokine therapies, may be needed to modulate the degree of immune activation.

At least two doses of tocilizumab per patient must be available on site prior to dosing of pembrolizumab.

6.4.4.1 Cytokine Release Syndrome Management

For patients treated with CAR-T therapies, significant CRS can occur in more than one-half of patients, with the frequency of significant CRS depending on the underlying disease process and specific CAR-T product. In the treatment of MM, a CRS rate of 76% was observed in a phase I study of bb2121, an anti-BCMA CAR-T product, with the majority of events being grade 1 or 2 (70%); 6% were grade 3 events with no grade 4 or higher events observed¹. Similar findings were observed in other early phase anti-BCMA CAR-T studies^{47,48}.

Management of cytokine release syndrome has involved the selective use of anti-cytokine therapies and anti-inflammatories for those patients with moderate to severe CRS. For patients with mild CRS (grade 1-2), supportive care alone with antihistamines, antipyretics, intravenous fluids, and close monitoring may be sufficient. For patients with moderate to severe CRS (grade 3 or higher; certain grade 2 cases), additional measures may be needed including: tocilizumab (anti-IL-6 receptor antibody), anakinra (IL-1 receptor antagonist), and/or dexamethasone. Given the success of tocilizumab in modulating severity of CRS, patients with moderate to severe CRS should be treated with tocilizumab first if supportive measures alone are unable to control the CRS. Tocilizumab is given as weight-based dose of 8 mg/kg intravenously at time of clinical instability, with the decision to administer and the timing individualized on a case-by-case basis with close consultation between the principal investigator (PI) and/or clinical investigators on the study. In severe cases or for those cases refractory to tocilizumab, additional therapies may be needed including: additional doses of tocilizumab, dexamethasone, or other anti-inflammatory/cytokine therapies.

Common indications for tocilizumab include any of the following:

- Hemodynamic instability despite intravenous fluids, especially if requiring vasopressor support
- Worsening respiratory status, including increasing oxygen requirements and/or need for high-flow oxygen, face mask, or mechanical ventilation.
- Any other significant deterioration thought to be secondary to CRS despite medical management.
- Patients with CRS should also undergo evaluation for infection and other causes for fevers and organ dysfunction. Patients should be closely monitored and may need admission to an intensive care unit depending on the clinical situation.
- Grading of CRS utilizes the ASTCT consensus criteria⁴⁹. Refer to Appendix 4 for details.

6.4.4.2 Immune-effector Cell-associated Neurotoxicity Syndrome

Given that pembrolizumab may re-activate anti-BCMA CAR-T cells, there is a theoretical risk for development of immune-effector cell-associated neurotoxicity syndrome (ICANS).

Similar to CRS, ICANS is a well-described toxicity of CAR-T therapy and is also considered to be a result of excessive immune activation. Clinical symptoms include: altered levels of consciousness, impairment of cognitive function, aphasia, seizures, and cerebral edema. The typical onset of neurologic toxicity is usually within several days after onset of CRS but may occur independently of CRS. In the phase I study of the anti-BCMA CAR-T bb2121, 14 patients (42%) reported neurologic toxic effects, with 13 patients (39%) incurring grade 1 or 2 toxicities and 1 patient (3%) having grade 4 toxicity¹. Similar rates were observed in early phase studies of other anti-BCMA CAR-T therapies^{47,48}.

Treatment for ICANS depends on severity of presentation. The ASTCT criteria are useful for risk-stratifying patients (refer to Appendix 5)⁴⁹. In general, patients with Grade 1 toxicity can be treated with supportive care and close monitoring (including frequent neurologic exams and assessment). Patients with Grade 2 or higher toxicity may require IV steroids, with dexamethasone 10 mg IV q6-12 hours as a standard front-line therapy. The use of other anti-inflammatories, including tocilizumab may be considered, especially if there is concurrent CRS. Additional workup including neuroimaging, electroencephalogram, and pupillometry may be indicated. Other supportive measures may include the addition of antiepileptics and in severe cases, transfer to the intensive care unit. Ultimately, each case of ICANS will be assessed and treated on a case-by-case basis, and any interventions to address ICANS, including the use of steroids, is acceptable when deemed medically appropriate by the treating physician in close consultation between the principal investigator (PI) and/or clinical investigators on the study.

6.5 Dietary Restrictions

Participants should maintain a normal diet unless modifications are required to manage an AE such as diarrhea, nausea, or vomiting.

6.6 Participant Discontinuation Criteria

When a participant discontinues prior to trial completion, all applicable activities scheduled for the final trial visit should be performed at the time of discontinuation. Any adverse events which are present at the time of discontinuation should be followed in accordance with the safety requirements outlined in Section 8.3.

Discontinuation of study intervention does not represent withdrawal from the study.

Participants may discontinue study treatment at any time for any reason or be dropped from the study treatment at the discretion of the investigator should any untoward effect occur. In addition, a participant may be discontinued from study treatment by the investigator or the Sponsor if study treatment is inappropriate, the trial plan is violated, or for administrative and/or other safety reasons. Specific details regarding procedures to be performed at study treatment discontinuation are provided in the subsequent sections.

A participant may be discontinued from study treatment but continue to be monitored in the study for any of the following reasons:

- The participant or participant's legally acceptable representative requests to discontinue study treatment.
- Any progression or recurrence of any malignancy, or any occurrence of another malignancy that requires active treatment.
- Unacceptable adverse experiences/dose-limiting toxicities including:
 - Grade 3 or higher immune-related AE that warrant discontinuation as outlined in Table 5.2-1

- Grade 3 or higher infusion reaction as outlined in Table 5.2-2
- Grade ≥ 3 CRS not responsive to tocilizumab therapy and/or best medical care after 72 hours or grade 4 CRS
- Grade ≥ 3 ICANS not responsive to best medical care after 72 hours or grade 4 ICANS
- Recurrent grade 2 pneumonitis
- The participant has a medical condition or personal circumstance which, in the opinion of the investigator and/or sponsor, placed the participant at unnecessary risk from continued administration of study treatment.
- The participant has a confirmed positive serum pregnancy test
- Noncompliance with study treatment or procedure requirements
- The participant is lost to follow-up
- Completion of 35 treatments (approximately 2 years) with pembrolizumab
- Administrative reasons

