5.2.1 Dose modification for cytokine release syndrome (CRS)

For participants who develop cytokine release syndrome grades 1-3 after pembrolizumab, further doses of pembrolizumab will be held until CRS completely resolves. Once CRS has fully resolved, the clinical investigator may resume pembrolizumab 200 mg every 3 weeks. Pembrolizumab will be discontinued for participants who develop grade 4 CRS or any grade 3 CRS that does not resolve to Grade \leq 1 or baseline within 48 hours with tocilizumab therapy and/or best medical care.

Guidelines for the management of patients who develop CRS, including the use of tocilizumab, are outlined in Section 6.4.4.1.

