5.2.2 Dose modification for immune-effector cell-associated neurotoxicity (ICANS)

For participants who develop immune-effector cell-associated neurotoxicity grades 1-3 after pembrolizumab, further doses of pembrolizumab will be held until symptoms resolve. Once ICANS has fully resolved, the clinical investigator may resume pembrolizumab 200 mg every 3 weeks. Pembrolizumab will be discontinued for participants who develop grade 4 ICANS or any grade 3 ICANS that does not resolve to Grade \leq 1 or baseline within 48 hours with steroids, tocilizumab therapy, and/or best medical care.

Guidelines for the management of patients who develop ICANS, including the use of tocilizumab and steroids, are outlined in Section 6.4.4.2.

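### Section 6.6 lists a 72-hour stopping criterion for grade 3 CRS and ICANS that does not match the mandatory 48-hour rule in Sections 5.2.1 and 5.2.2

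*Combined protocol and SAP*

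**What the plan says.** The stop rule for CRS is in Section 5.2.1: "Pembrolizumab will be discontinued for participants who develop grade 4 CRS or any grade 3 CRS that does not resolve to Grade" ≤1 "or baseline within 48 hours with tocilizumab therapy and/or best medical care". Section 5.2.2 opens its ICANS rule in the same way, "Pembrolizumab will be discontinued for participants who develop grade 4 ICANS or any grade 3 ICANS that does not resolve to Grade" ≤1 or baseline, again with a 48-hour limit. Both sections hold further doses after grade 1 to 3 events and let the investigator resume after full resolution.

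Section 9.2 uses the 48-hour, Grade ≤1 or baseline criterion for both toxicities, but to pause enrollment for safety review rather than to stop an individual's treatment.

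Section 6.6 opens its list with "A participant may be discontinued from study treatment but continue to be monitored in the study for any of the following reasons". Among the dose-limiting toxicities it gives grade 3 or higher "CRS not responsive to tocilizumab therapy and/or best medical care after 72 hours or grade 4 CRS" and grade 3 or higher "ICANS not responsive to best medical care after 72 hours or grade 4 ICANS". Two neighbouring entries point back to Section 5.2: "Grade 3 or higher immune-related AE that warrant discontinuation as outlined in Table 5.2-1" and "Grade 3 or higher infusion reaction as outlined in Table 5.2-2". The CRS and ICANS entries do not.

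**The concern.** CRS and ICANS from reactivated CAR-T cells are the toxicities specific to this trial. Section 1.4 names them as added risk, and Section 5.1 requires tocilizumab on site before dosing. Their stopping rule should read the same wherever it appears.

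Section 6.6 is also a natural place to look it up. Sections 3.1 and 5.1 continue treatment until progression or dose-limiting toxicity, and 6.6 is where that term is itemised. A reader arriving that way finds a later time point and a weaker recovery test than the mandatory rule. At stake is whether a participant with a slowly resolving grade 3 event is permanently stopped, as 5.2 requires, or is treated as eligible to resume.

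**Working it through.** No arithmetic settles this. The check is a comparison of the rules.

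| Feature | 5.2.1 and 5.2.2 | 9.2 | 6.6 |
|---|---|---|---|
| Time limit for grade 3 | 48 hours | 48 hours | 72 hours |
| Recovery test | Grade ≤1 or baseline | Grade ≤1 or baseline | response to treatment, not defined |
| Grade 4 | stop | pause enrollment | listed |
| Force | mandatory for the participant | mandatory pause of enrollment | permissive, list not exhaustive |

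Because grade 4 is listed in its own right in 6.6, the 72-hour clause matters in practice only for grade 3. Applying 5.2 and 6.6 to each possible course:

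1. **Grade 4.** Mandatory stop under 5.2, listed in 6.6. They agree.
2. **Grade 3, fully resolved within 48 hours.** Held and then resumable under 5.2; 6.6 entry not met. They agree.
3. **Grade 3, reaching Grade ≤1 at 60 hours.** Mandatory stop under 5.2; 6.6 entry not met. They differ.
4. **Grade 3, improved to grade 2 but still grade 2 at 48 hours.** Mandatory stop under 5.2. Under 6.6 it depends on what counts as a response, and improvement by one grade could reasonably qualify. They can differ.
5. **Grade 3, no improvement by 72 hours.** Mandatory stop under 5.2, listed in 6.6. They agree on the event, though only 5.2 compels the stop.

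The mismatch is therefore confined to courses 3 and 4.

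**How often.** The documents give no rate or time to resolution for grade 3 CRS or ICANS after pembrolizumab in this population. The indirect figures point in different directions:

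- Pembrolizumab after CD19 CAR-T in lymphoma (Section 1.5): the only grade 3 or higher event type was neutropenia, so 0 of 12 had grade 3 or higher CRS or ICANS. The exact 95% upper limit is 1 − 0.025^(1/12) = 26.5%.
- Atezolizumab started between Day 1 and Day 21 after axicabtagene ciloleucel (Section 1.5): grade 3 or higher CRS in 3 of 12 (25%) and grade 3 or higher neurologic events in 6 of 12 (50%), described as comparable to the CAR-T product alone.
- The anti-BCMA product bb2121 without pembrolizumab (Sections 6.4.4.1 and 6.4.4.2): 6% grade 3 CRS. Of 14 patients with neurotoxicity, 13 had grade 1 or 2 and 1 had grade 4, so 14 − 13 − 1 = 0 had grade 3.

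None of these matches the trial setting, and none says how many grade 3 events would follow course 3 or 4.

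**The case against.** The strongest reply is that both texts can be obeyed at once. Sections 5.2.1 and 5.2.2 are mandatory, while 6.6 is permissive, is not exhaustive, and nowhere tells anyone to continue or resume. Section 5.2 directs readers to 5.2.1 and 5.2.2 for these two toxicities. That stands, and it limits the point: a reader might infer that 6.6 relaxes or overrides the 48-hour rule, but nothing in it does so.

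Exposure is also partly contained. Doses are held until full resolution and given every 3 weeks, so the 72 − 48 = 24-hour gap does not itself produce a dose. Every disputed event pauses enrollment under 9.2. The authority to resume sits in 5.2.1 and 5.2.2 beside the 48-hour rule, so a wrong resumption requires someone to judge the stop from 6.6 alone. All of this stands too. Yet the hold ends at resolution, and the 9.2 pause concerns enrollment rather than the affected participant's next dose. For a slow grade 3 event, the 48-hour rule is what makes the stop compulsory.

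Three stronger readings are tempting and are not supported:

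- **The discontinuation endpoint is distorted.** Section 2.3 counts treatment discontinuations due to toxicity and does not define them by the 6.6 entries. A participant stopped under 5.2 counts either way, so the count changes only if 5.2 is breached.
- **The response rate is affected.** Section 6.8 excludes and replaces participants who stop for toxicity before 4 cycles, so a link could be imagined. It too would need a breach of 5.2.
- **The re-challenge provision in 8.5 must also be amended.** It covers selected events, subject to the investigator's judgment of safety and ethics, and does not claim to override 5.2. A general bar there would set policy for every toxicity in Section 5.2, which is a separate question.

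**Conclusion.** The CRS and ICANS entries in 6.6 are wrong as written. They differ from the mandatory rule in time limit and recovery test, and no section reconciles them. The scope is narrow: grade 3 events that resolve between 48 and 72 hours, or that improve but are not at Grade ≤1 or baseline by 48 hours. The consequence is a risk of inconsistent application, namely resuming pembrolizumab after resolution in a participant whom 5.2 requires to be discontinued.

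No number can be put on this. The documents support neither a claim that such events are rare nor a claim that they are common. This conclusion assumes that 5.2.1 and 5.2.2 state the intended rule. They are mandatory, they define recovery, and 9.2 uses the same criterion. If they are followed, neither the overall response rate nor the discontinuation endpoint is affected.

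**What to change.** Replace the two 72-hour bullets in Section 6.6 with:

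- *Grade 4 CRS, or grade 3 CRS that does not resolve to Grade ≤1 or baseline within 48 hours, as outlined in Section 5.2.1*
- *Grade 4 ICANS, or grade 3 ICANS that does not resolve to Grade ≤1 or baseline within 48 hours, as outlined in Section 5.2.2*

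This follows the cross-reference style of the neighbouring bullets. Sections 5.2.1, 5.2.2, 8.5 and 9.2 stay as they are. The cost is a wording amendment to two bullets, with no change to sample size, visits or analysis.

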6.7 Participant Withdrawal from Study

Participants who withdraw prior to completion of the trial should be encouraged to complete all applicable activities scheduled for the final study visit at the time of withdrawal. Any AEs that are present at the time of withdrawal should be followed in accordance with the safety requirements outlined in Section 8.3.

A participant must be withdrawn from the study if the participant or the participant's legally acceptable representative withdraws consent from the study.

A participant may also be withdrawn from the study for the following reasons:

- Progressive disease
- Start of new anti-cancer therapy
- Noncompliance with study treatment or procedure requirements
- The participant is lost to follow-up
- Investigator decision

If a participant withdraws from the study, they will no longer receive study intervention or be followed at scheduled protocol visits.

Specified details regarding procedures to be performed at the time of withdrawal from the study are outlined in Section 6.3.3.

6.8 Participant Replacement Strategy

If a participant is enrolled but does not receive any doses of pembrolizumab, the participant may be replaced.

If a participant is enrolled and receives less than 4 cycles of therapy and discontinues therapy or withdraws from the study for reasons other than disease progression, the participant will not be evaluated for the primary efficacy endpoint and will be replaced. However, all participants who receive at least one dose of pembrolizumab will be included in the safety analysis for adverse events (including those that received < 4 cycles of therapy).

6.9 Clinical Criteria for Early Trial Termination

Early trial termination will be the result of the criteria specified below:

1. Quality or quantity of data recording is inaccurate or incomplete
2. Poor adherence to protocol and regulatory requirements
3. Incidence or severity of adverse drug reaction in this or other studies indicates a potential health hazard to participants
4. Plans to modify or discontinue the development of the study drug

In the event of Merck's decision to no longer supply study drug, adequate notification will be provided so that appropriate adjustments to participant treatment can be made.

7 Reporting and Documentation of Results

7.1 Evaluation of Efficacy: Antitumor Effect – Hematologic Tumors

Measurement of antitumor effect will be primarily through tumor markers (SPEP/SPIE, FLC, UPEP/UPIE, and bone marrow biopsy [where applicable]) as per International Myeloma Working Group (IMWG) Uniform Response Criteria. Only participants that complete at least 4 cycles of therapy or have progressive disease after at least one cycle of therapy will be included in the analysis for the primary endpoint. See Appendix 6 for additional details.

7.1.1 Methods for Evaluation of Measurable Disease

For participants with measurable disease by M-protein (serum M-protein ≥ 1 g/dL), response criteria will be determined primarily by SPEP/SPIE. For participants with measurable disease by 24-hour UPEP/UPIE (≥ 200 mg/24 hours) but not by SPEP/SPIE (M-protein < 1 g/dL), response criteria will be determined primarily by UPEP/UPIE. For participants with only measurable disease by FLC and without measurable disease by SPEP/SPIE and UPEP/UPIE, response criteria will be determined primarily by FLC levels.

Participants will also undergo 24-UPEP/UPIE at certain time points depending on 24-hour UPEP/UPIE at screening.

- Participants who have measurable disease by SPEP/SPIE (M-protein ≥ 1 g/dL) and by 24-hour UPEP/UPIE (≥ 200 mg/24 hours) at screening will undergo a 24-hour UPEP/UPIE at time of suspected sCR, CR, VGPR, PR, and progressive disease.
- Participants with measurable disease by SPEP/SPIE (M-protein ≥ 1 g/dL) but no measurable 24-hour UPEP/UPIE (< 200 mg/24 hours) at screening will undergo a 24-hour UPEP/UPIE at time of suspected sCR, CR, VGPR, and progressive disease to confirm IMWG response criteria.
- Participants with only measurable disease by FLC and without measurable disease by SPEP/SPIE and UPEP/UPIE at screening will undergo 24-hour UPEP/UPIE at time of suspected sCR, CR, VGPR, and progressive disease.

For participants who develop serologic markers consistent with a complete response (disappearance of serum and urine M-protein on electrophoresis for patients with measurable M-protein at treatment initiation or normalization of the free light chain ratio for those with

elevated free light chain markers but unmeasurable M-protein at treatment initiation), a bone marrow biopsy is required to confirm IMWG complete response.

For participants with known soft tissue plasmacytomas or extramedullary disease on enrollment, imaging (PET/CT, CT, or MRI) is recommended to confirm IMWG response for patients who achieve at least a hematologic partial response. Imaging is also recommended if there is clinical concern for progressive disease.

7.1.2 Response Criteria

The primary endpoint is the overall response rate (ORR), defined as the proportion of patients achieving a partial response (PR) or better (including sCR, CR, and VGPR) after 4 cycles of pembrolizumab therapy. The response criteria are described below (see Appendix 6 for additional details) :

- Stringent complete response (sCR)
 - Requires achieving complete response (CR) defined below plus normal FLC ratio and absence of clonal plasma cells by immunohistochemistry or flow cytometry
- Complete response (CR)
 - *For patients with measurable serum or urine M-protein on enrollment:* negative immunofixation of serum and urine and < 5% plasma cells in the bone marrow is required
 - *For patients without measurable serum and urine M-protein levels on enrollment:* a normal FLC ratio (0.6 – 1.65) is necessary in addition to the above criteria
 - *For patients with known soft tissue plasmacytomas or extramedullary disease on enrollment,* disappearance of all soft tissue plasmacytomas is required to meet CR
- Very good partial response (VGPR)
 - *For patients with measurable serum or urine M-protein on enrollment:* detectable M-protein on immunofixation but not on electrophoresis or ≥ 90% reduction in serum M-protein plus urine M-component < 100 mg/24 hours is required.
 - *For patients without measurable serum and urine M-protein levels on enrollment (only measurable disease is by serum FLC):* ≥ 90% decrease in the difference between involved and uninvolved free light chains is required.
- Partial response (PR)
 - *For patients with measurable serum and urine M-protein on enrollment:* ≥ 50% reduction of serum M-protein and reduction in 24-hour urinary M-protein by ≥ 90% to < 200 mg/24 hours are required.
 - *For patients with measurable serum but without measurable urine M-protein on enrollment:* ≥ 50% reduction of serum M-protein is required.
 - *For patients without measurable serum and urine M-protein levels on enrollment (only measurable disease is by serum FLC):* ≥ 50% decrease in the difference between involved and uninvolved free light chains is required (provided the

serum-free light chain assay shows involved level > 10 mg/dL and the serum-free light chain is abnormal).

- *For patients with known soft tissue plasmacytomas or extramedullary disease on enrollment, $\geq 50\%$ reduction in size of soft tissue plasmacytomas is required in addition to the above criteria.*
- Stable Disease (SD)
 - Not meeting criteria for sCR, CR, VGPR, PR, or PD
- Progressive Disease (PD)

Meeting one of the following criteria:

- Increase of $\geq 25\%$ from the lowest response value achieved in one or more of the following:
 - serum M-protein: absolute increase must be ≥ 0.5 g/dL)
 - Urine M-component (absolute increase must be ≥ 200 mg/24h)
 - *Only in patients without measurable serum and urine M-protein levels at enrollment:* the difference between involved and unininvolved FLC levels (absolute increase must be > 10 mg/dL)
- Definite development of new bone lesions or soft tissue plasmacytomas or definite increase in the size of existing bone lesions or soft tissue plasmacytomas
- Development of hypercalcemia (corrected serum calcium 11.5 mg/dL) that can be attributed solely to the plasma cell proliferative disorder.

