Appendix 6 IMWG Uniform Response Criteria

Response	IMWG criteria ⁴⁶
Stringent complete response (sCR)	CR as defined below plus normal FLC ratio and absence of clonal plasma cells by immunohistochemistry or flow cytometry
Complete response (CR)	Negative immunofixation of serum and urine and disappearance of any soft tissue plasmacytomas and < 5% plasma cells in bone marrow. For patients without measurable serum and urine M-protein levels at baseline: a normal FLC ratio (0.6 – 1.65) is necessary in addition to the above criteria
Very good partial response (VGPR)	Serum and urine M-component detectable by immunofixation but not on electrophoresis or ≥90% reduction in serum M-component plus urine M-component < 100 mg/24 hours For patients without measurable serum and urine M-protein levels at baseline: ≥90% decrease in the difference between involved and uninvolved free light chains
Partial response (PR)	≥ 50% reduction of serum M-protein and reduction in 24-hour urinary M-protein by ≥ 90% to < 200 mg/24 hours. If serum and urine M-protein are not measurable, a decrease ≥50% in the difference between involved and uninvolved FLC levels is required in place of the M-protein criteria. If serum and urine M-protein are not measurable, and serum-free light assay is also not measurable, ≥ 50% reduction in bone marrow plasma cells is required in place of M-protein, provided baseline percentage ≥ 30%. In addition to the above criteria, if present at baseline, ≥50% reduction in the size of soft tissue plasmacytomas is also required.
Stable Disease (SD)	Not meeting criteria for CR, VGPR, PR, or PD

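### VGPR carries no plasmacytoma condition although PR and CR do, so a participant whose baseline lesion has not shrunk enough for PR can still count as a responder in the primary ORR

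*Combined protocol and SAP*

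**What the plan says.** Section 7.1.2 defines the primary endpoint as the proportion "achieving a partial response (PR) or better (including sCR, CR, and VGPR) after 4 cycles of pembrolizumab therapy". It then sets out the categories.

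- **CR:** for known soft tissue plasmacytoma or extramedullary disease, "disappearance of all soft tissue plasmacytomas is required to meet CR". sCR is built on CR and so inherits this.
- **VGPR:** for M-protein disease, "detectable M-protein on immunofixation but not on electrophoresis or ≥ 90% reduction in serum M-protein plus urine M-component < 100 mg/24 hours is required". For disease measurable only by free light chains (FLC), a fall of at least 90% in the FLC difference. Neither bullet mentions plasmacytomas.
- **PR:** marker criteria, and for known plasmacytoma or extramedullary disease a 50% or greater "reduction in size of soft tissue plasmacytomas is required in addition to the above criteria".
- **PD:** among other criteria, new lesions or definite growth of existing ones.
- **SD:** whatever meets none of the other categories, VGPR included.

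Appendix 6 repeats the pattern. Its VGPR row begins "Serum and urine M-component detectable by immunofixation but not on electrophoresis or ≥90% reduction in serum M-component plus urine M-component" and has no lesion condition. Its PR row ends "In addition to the above criteria, if present at baseline, ≥50% reduction in the size of soft tissue plasmacytomas is also required".

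**The concern.** The categories are meant to run in order of depth, and the endpoint treats them that way by counting PR and everything above it. For participants with a baseline plasmacytoma the order breaks: the lesion condition applies at PR, disappears at VGPR and returns at CR. The same lesion finding blocks a response at one marker depth and is ignored at the next.

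The decision rules turn on single participants. Stage 1 stops at 1 of 15 and continues at 2. The final test fails at 5 of 25 (20%) and succeeds at 6 (24%). A responder rule that is inconsistent for an eligible subgroup, and can err only towards more responders, matters at those boundaries. It is better settled before an actual case has to be classified with its effect on the result already visible.

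**Working it through.** **Wording check.** Take a participant with measurable serum M-protein, no measurable urine M-protein, and a plasmacytoma at enrollment. Suppose imaging shows it unchanged or shrunk by less than 50%.

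| Serum M-protein fall | PR | VGPR | PD | Category | Counts in ORR |
|---|---|---|---|---|---|
| 60% | fails on lesion | fails on marker | no | SD | no |
| 90% or more, urine below 100 mg/24 h | fails on lesion | met as written | no | VGPR | yes |

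PD does not catch the second row, because the lesion has not grown. SD does not, because meeting VGPR excludes SD. A fall of at least 90% in the FLC difference opens the same route for FLC-only disease. Complete imaging does not change the result. The case can occur: inclusion criterion 7 accepts biopsy-proven extramedullary plasmacytoma, and no exclusion criterion removes it.

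**Design figures reproduced.** Inputs from section 9.1.1: 15 participants in stage 1, stop at 0 or 1 response; 25 in total, reject at 6 or more; null 10%, alternative 30%. Let X1 ~ Bin(15, p) and X2 ~ Bin(10, p).

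- Early stopping = P(X1 ≤ 1). At p = 0.10: 0.9^15 + 15 × 0.1 × 0.9^14 = 0.206 + 0.343 = 0.549 (plan: 55%).
- Rejection = Σ over x = 2 to 15 of P(X1 = x) × P(X2 ≥ 6 − x). At p = 0.10: 0.0328 (plan's limit: 5%). At p = 0.30: 0.802 (plan: 80%).

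**Unconditional effect.** The documents give neither the share with extramedullary disease (e) nor the share of those who are discordant (d), meaning a VGPR-level marker fall with a lesion that fails PR. Assumed: e = 20-40%, d = 2-10%. Leakage is e × d, added to a true 10% ORR.

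| Leakage (points) | Example | Type I error | Early stopping | At least one case in 25 |
|---|---|---|---|---|
| 0 | none | 3.3% | 54.9% | 0% |
| 0.4 | 20% × 2% | 3.9% | 52.8% | 10% |
| 0.8 | 40% × 2% | 4.5% | 50.7% | 18% |
| 1 | 20% × 5% | 4.9% | 49.7% | 22% |
| 2 | 20% × 10% | 7.0% | 44.8% | 40% |
| 4 | 40% × 10% | 12.5% | 35.8% | 64% |

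The last column is 1 − (1 − leakage)^25. Solving for a rejection probability of 5% gives p = 0.1105, that is, leakage of about 1.05 points.

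**Conditional effect.** Suppose exactly one such participant has occurred and all others respond at 10%.

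- Case in stage 1: the trial stops only if none of the other 14 responds, 0.9^14 = 0.229. Rejection = Σ over x = 1 to 14 of P(Bin(14, 0.1) = x) × P(Bin(10, 0.1) ≥ 5 − x) = 0.0847.
- Case in stage 2: rejection = Σ over x = 2 to 15 of P(Bin(15, 0.1) = x) × P(Bin(9, 0.1) ≥ 5 − x) = 0.0820.

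**The case against.** **The participant is counted as the endpoint prescribes.** VGPR is named in the endpoint, and this participant meets its text. That stands: a reader might infer a miscount, but the documents support only an inconsistent rule. One could also read the endpoint as implying that VGPR includes PR. No sentence says so, and where the protocol wants one category built on another (sCR on CR) it states it.

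**The table is labelled as IMWG criteria, with a citation.** The wording may be inherited. That cannot be checked from these documents, so it should not be inferred that the protocol misquotes its source. An added lesion condition could be a departure from that source and should be presented as a protocol clarification. Inheritance would not remove the inconsistency within this protocol.

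**Intent to check lesions is partly documented.** Section 7.1.1 recommends imaging for participants with known extramedullary disease who reach at least a hematologic PR, which covers VGPR. Growing or new lesions are PD. It would therefore be wrong to infer that a participant with documented lesion growth counts as a responder. This narrows the gap to lesions that are stable or have shrunk by less than 50%; it does not close it. The imaging is optional, and no size threshold is attached to VGPR.

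**The effect may be very small.** This also stands. At 2% discordance the type I error stays at 3.9-4.5% over the whole assumed extramedullary range. The upper end is demanding: it adds marker-deep, lesion-discordant cases to a 10% true rate, while the only single-agent PD-1 myeloma trial that section 1.1 reports had one responder in 27.

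**Conclusion.** Wrong as written: the responder rule for the primary endpoint is internally inconsistent for participants with a baseline plasmacytoma. Severity is minor to moderate. That the gap exists, and that it can only add responders, follows from the text alone. Its size does not: the 3.9-12.5% range rests wholly on the assumed 20-40% extramedullary share and 2-10% discordance.

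A reader might take 8.2-8.5% as the trial's type I error, or 23% as its early stopping probability. Neither is a property of the design. Both apply only once one discordant case has occurred, and the 23% only if that case is in stage 1. The sample size, boundaries and stated operating characteristics are correct and need no change.

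**What to change.** Add to section 7.1.2 and Appendix 6:

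1. For the primary ORR, a participant with soft tissue plasmacytoma or extramedullary disease at enrollment counts as a responder in any category, VGPR included, only if the plasmacytoma reduction required for PR is also met.
2. Such a participant without response imaging is not counted as a responder.
3. This is a protocol clarification of the tabulated IMWG criteria. ORR with VGPR classified on markers alone is reported as a sensitivity analysis.

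Point 2 is needed because section 7.1.1 only recommends imaging, Appendix 6 says radiographic studies are not required, and the study calendar lists none. Without it the lesion condition could not be applied to everyone concerned, and PR already has the same difficulty.

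Cost: a few sentences in two places. The ORR may be slightly lower, both from discordant cases and from unimaged participants. The lesion measurements are those the PR rule already needs, but in affected participants the recommended imaging becomes a condition of being counted as a responder. The 25 participants, the 2-of-15 and 6-of-25 thresholds, and the power and type I error calculations stay as they are.
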